5. STUDY PROCEDURES

5.1 Study Site

Study participants will be selected from Mass General Brigham (MGB), a large integrated delivery network in Boston, MA, specifically from Mass General Hospital primary care clinics, where [name] practices.

5.2 Overall Design

We will use the Mass General Brigham COVID-19 Vaccine Registry and EHR information in the Research Patient Data Registry (RPDR) and/or Epic Enterprise Data Warehouse (EDW) to identify all patients age ≥ 18 with an upcoming primary care outpatient appointment who are eligible for the COVID booster vaccine. We plan to launch the study after the booster vaccine has become widely available to adults over age 18 and supply of vaccines at MGB is anticipated to be sufficient. All eligible patients will be randomized to one of three arms: 1) “why” messaging, 2) “how” messaging, or 3) standard of care (“usual care”). We will conduct stratified randomization based on the primary care clinic the patient attends and day of the week the upcoming visit is on.

The primary outcome will be the rate of booster vaccination at the targeted visit. Secondary outcome will be receipt of a booster vaccine within 6 weeks of the target visit at any location. After completion of the trial, we will utilize data from the RPDR and/or EDW to develop models that predict which patients are most likely to respond to each intervention using patient baseline characteristics, which in the future could allow for targeting of interventions to specific patients. We will use the Mass General Brigham COVID-19 Vaccine Registry and the RPDR/EDW for outcome measurement.

5.2.1 Aim 1 Design

[figure not shown]
In Aim 1 of the study, we will conduct a 3-arm randomized controlled trial to compare the effectiveness of two interventions compared to usual care on COVID-19 vaccination uptake. We will include Mass General Brigham (MGB) patients age ≥ 18 with an upcoming primary care outpatient visit with a Mass General Hospital primary care provider who are eligible for the COVID booster vaccine and who have not received a dose. This approach has been approved by MGH primary care leadership. Patients will be excluded if they did not receive the full set of their primary COVID-19 series.

Patients will be randomized equally to one of three arms: 1) “why” messaging, 2) “how” messaging, or 3) standard of care (“usual care”). We plan to conduct stratified randomization based on the primary care clinic the patient attends to account for differences in patient populations between clinics and based on the day of the week the upcoming visit is on to minimize logistic difficulties in the intervention delivery. “Why” messages will focus on reasons to get the vaccine, including protecting self and loved ones or the idea of herd immunity. “How” messages will focus on the details of obtaining a vaccination at MGB, what to expect, and how to prepare for the visit. The messages will be sent through the EHR electronic patient portal for portal users. For patients whose primary language listed in the EHR is not English, they will be offered translated messages following standard MGB Gateway messaging practices. Gateway messages will first include a message translated in their primary language (Spanish, Portuguese, Arabic, Chinese, Russian, Haitian Creole or Bosnian) followed by an English version of the message. Consistent with recent studies for influenza vaccination and the approach approved by MGH primary care leadership, we will send a message to patients a few days in advance of their office visit.¹⁶ Based on current MGH practice (i.e., standard of care), patients in Arm 3 will not receive any additional message about their upcoming visit, beyond what they already receive by MGH. **Initial examples of these messages are attached.**

5.2.2 Aim 2 Design

In Aim 2, we will assess association of clinical and demographic characteristics with intervention responsiveness. To do this, we will measure baseline patient clinical, historical, and demographic characteristics. Characteristics measured from the RPDR/EDW will include age, gender, race, prior influenza vaccine history, and comorbidities that increase risk of severe COVID disease, among others. We will also measure zip-code linked variables including mean household income, education level, rurality, and prevalence of COVID in the patient's surrounding community. We will develop models that predict which patients are most likely to respond to each intervention using patient baseline characteristics, which in the future could allow for targeting of interventions to specific patients.

5.3 Study Schema

5.4 Scientific rationale for study design

The use of a randomized trial design will be able to both provide stronger evidence of causality in the effectiveness of the interventions and allow for empiric derivation of patient characteristics that may influence intervention responsiveness. An observational study design or patient self-report of factors that influence intervention responsiveness are more subject to bias.

5.5 Justification for intervention

According to Construal Level Theory, emphasizing “why” elicits more abstract thinking, or high-level construals, and can induce an emotional mindset, which could challenge an individual’s sense of identity, autonomy, or political preferences. Conversely, emphasizing “how” is more cognitive and evokes concrete thinking, or low-level construals, and encourages a planning or implementation mindset.^{10,11} Low-level construals (“how” messages) have been shown to increase intention to or uptake of several health behaviors including dietary changes,¹² use of relaxation techniques,¹³ blood donation,¹⁴ and completion of biometric screening and health surveys.¹⁵ Though prior studies of vaccine acceptance have not explicitly applied Construal Level Theory, aspects of interventions that elicit low-level construals have been successful compared to other techniques.

Because of the political and emotional valence of the COVID-19 vaccine, “how” messaging to elicit concrete thinking may be particularly important. Direct comparison of “how” vs “why” messages has not been tested for vaccines, and it has never been tested for COVID-19. Moreover, COVID vaccine hesitancy differs by age, gender, and race,^{4,6} and demographic groups may respond differently to messages. Tailoring a message to a specific group with higher rates of vaccine hesitancy could help reduce health disparities.

5.6 End-of-study definition

The active interventions in Aim 1 are expected to last no more than 1 week. The study data collection of vaccination receipt will begin after the target primary care outpatient visit will conclude 1 month after the target visit is complete, as we anticipate some lag for complete vaccination information to be included in the MGB COVID-19 Vaccine Registry data source. Development of the prediction models will be done following Aim 1 data collection.

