2. SPECIFIC AIMS

The main aims are to 1) test the effect of “how” vs “why” framed messages on the rates of COVID-19 booster vaccination and 2) assess association of clinical and demographic characteristics with intervention responsiveness.

The objectives and endpoints for this project are summarized below.

OBJECTIVES	ENDPOINTS	JUSTIFICATION FOR ENDPOINTS
Aim 1		
To test the effect of “how” vs “why” framed messages on the rates of COVID-19 vaccination	Primary : the rate of booster vaccination at the targeted visit Secondary : the rate of receipt of a COVID booster vaccine within 6 weeks of the targeted visit	These outcomes are directly related to the interventions, are clinically meaningful, and are measurable using routinely collected data in the Mass General Brigham COVID-19 Vaccine Registry and the Research Patient Data Registry (RPDR) and/or Epic Enterprise Data Warehouse (EDW). We plan to use RPDR for variable collection as long as all the variables needed are available in the RPDR. If a variable is not available in the RPDR then we will supplement with use of the EDW for those variables.
Aim 2		
To assess association of clinical and demographic characteristics with intervention responsiveness	A model to predict likelihood of response to each intervention based on patient characteristics	A model predicting intervention responsiveness could be used to tailor future interventions to specific patients

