4.3 Treatment assignment and randomization

All eligible patients will be randomized to one of three arms: 1) “why” messaging, 2) “how” messaging, or 3) “standard of care (“usual care”). We plan to conduct stratified randomization based on the primary care clinic the patient attends to account for differences in patient populations between clinics. We will also use block-stratified randomization, in which the unit of randomization is the day of the week the study visit is on. This choice was made in response to the logistical difficulties randomizing at the patient level presented. Each weekday, eligible patients will be identified that have an upcoming visit 2-3 days from then. The day of the week of that visit will be randomized in a 1:1:1 ratio with a random number generator to one of three arms: 1) “why” messaging, 2) “how” messaging or 3) “standard of care” (“usual care”).

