5.7 Data sources

Sources of research material, data that will be recorded, when data will be collected

Data regarding patients' medical history, disease control, medication use and health care utilization will be obtained from The Mass General Brigham COVID-19 Vaccine Registry and EHR data from the Research Patient Data Registry (RPDR) and/or Enterprise Data Warehouse (EDW), supported by Epic Systems, Inc.

The Mass General Brigham COVID-19 Vaccine Registry is a secure repository of data containing COVID-19 vaccine administration, utilization and adverse event information for analysis by the research community. This registry contains identified patient vaccination data for patients with a record of any type or dose of the COVID-19 vaccine. The data lives on a secure server within the Mass General Brigham firewall. It is only accessible to IRB-approved researchers. The data in the registry is updated every week. Its usage is logged and audited.

The Enterprise Data Warehouse for Epic EHR data resides in an Oracle 9i environment and consists of the Clarity and Payer databases. The Clarity database is a relational database that contains clinical and financial information from the Epic Suite of products; including the electronic medical record system (EpicCare), the appointment scheduling system (Cadence), the patient accounting system (Resolute), the patient web portal and the master patient index (Identity). The various tables within the Clarity database are refreshed on a daily, weekly or monthly basis. The data extracts obtained from the RPDR/EDW are maintained on secure MGB servers housed at the Division of Pharmacoepidemiology in the Department of Medicine at BWH.

Linkages to subjects, access to subject identities

Individually identifiable data are required to link patients between the Mass General Brigham COVID-19 registry and the RPDR/EDW, and to send messages to patients as part of this trial. Without this linkage, we could not fulfill the study's objectives. To protect the confidentiality of these data, only the minimal necessary research staff will have access to personal identifiers. After the intervention is completed and study variables are created, all identifiable information will be deleted from the study database. All research staff are properly trained in research management and will be approved by the IRB. All personally identifiable health information will be kept under lock and key.

Schedule of activities

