6.4 Samples size determination

Sample size estimates suggest that ~1,100 individuals in each arm will allow us to observe a 5% difference in vaccination rates compared to the usual care arm, assuming a usual care arm vaccination rate of 20% as well as assumptions of alpha=0.05 and power=0.80. Given that more than 1 million patients receive care at MGB, we expect to identify at least 5,000 patients who have not yet received the booster vaccination at the outset of the trial and who will be eligible to receive one of the messages. This will also provide sufficient power for secondary outcomes. Under the same assumptions, we should be able to observe a <6% difference in 6-week vaccination rates compared to usual care, assuming a usual care arm vaccination rate of 25%.

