6.5.2 Analysis of the secondary endpoints

Secondary outcomes will include in each arm the rate of receipt of COVID booster vaccine 6 weeks after the target primary care outpatient appointment. As in the primary analysis, we will use the MGB Research Patient Data Registry (RPDR) and/or Electronic Data Warehouse (EDW) for outcome measurement. We will use logistic regression to compare outcomes between each intervention arm versus usual care and against each other; in secondary analyses, we will additionally adjust for any imbalanced baseline characteristics.

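### Collection of vaccination receipt ends 1 month after the target visit, but the secondary endpoint runs to 6 weeks

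*Combined protocol and SAP*

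**What the plan says.** The end-of-study definition (Section 5.6) is the only available text that sets when collection of vaccination receipt stops. It starts collection after the target visit and says it "will conclude 1 month after the target visit is complete, as we anticipate some lag for complete vaccination information". The sentence appears to lack a conjunction, but the interval and its starting point are clear.

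Four other sections use 6 weeks:

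- Section 2 defines the secondary endpoint as "the rate of receipt of a COVID booster vaccine within 6 weeks of the targeted visit".
- Section 5.2: "Secondary outcome will be receipt of a booster vaccine within 6 weeks of the target visit at any location".
- Section 6.5.2 analyses "the rate of receipt of COVID booster vaccine 6 weeks after the target primary care outpatient appointment".
- Section 6.4 sizes it: "we should be able to observe a <6% difference in 6-week vaccination rates compared to usual care", with an assumed usual-care rate of 25%.

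Three further statements bear on timing. Enrolment is rolling (Section 4.3): "Each weekday, eligible patients will be identified that have an upcoming visit 2-3 days from then". Section 5.6 also says: "The active interventions in Aim 1 are expected to last no more than 1 week". On refresh, Section 5.7 says of the vaccine registry: "The data in the registry is updated every week". The same section has the Clarity tables refreshed daily, weekly or monthly, depending on the table.

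**The concern.** A 42-day endpoint cannot be fully observed if collection stops at day 28 to 31. Section 5.6 gives registry lag as the reason for the month. That makes sense for a primary endpoint fixed on the day of the visit, where the month is pure waiting time. For the secondary endpoint the same month ends before the window closes and leaves no time for late entries.

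If Section 5.6 were followed, the trial would report as a 6-week rate something that is nearer a 1-month rate, either for everyone or for an unstated fraction of patients. The loss could become permanent. Section 5.7 deletes identifiable information once the intervention is over and the study variables exist, and Section 9.5 removes identifiers once linkages are complete. After that, boosters given in weeks 5 and 6 could not be recovered by linking again.

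**Working it through.** **1. The plan's own figures.** Inputs from Section 6.4: about 1,100 per arm, alpha 0.05 (two-sided assumed, since the plan does not say), power 0.80, usual-care rates of 20% at the visit and 25% at 6 weeks. With the pooled-variance formula for two proportions,

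n = [1.96 × √(2 × 0.225 × 0.775) + 0.8416 × √(0.20 × 0.80 + 0.25 × 0.75)]² / 0.05² ≈ 1,094 per arm,

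which agrees with the stated 1,100. Solving the same formula at n = 1,100 from a 25% base gives a detectable difference of 5.34 points, consistent with the stated figure of under 6. The sample-size section is therefore sound and really is built on the 6-week rate.

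**2. The gap.** 6 weeks = 42 days and 1 month = 28 to 31 days.

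- 42 − 31 = 11 days; 11/42 = 26%.
- 42 − 28 = 14 days; 14/42 = 33%.

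**3. Month counted from each patient's visit.** Every patient loses the last 11 to 14 days. Assume the usual-care rate rises evenly from 20% to 25% over 42 days:

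- Captured by day 28: 20 + 5 × 28/42 = 23.3%, so 1.7 points are missed.
- Captured by day 31: 20 + 5 × 31/42 = 23.7%, so 1.3 points are missed.

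Less is missed if uptake is concentrated soon after the visit.

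**4. Month counted from the last visit in the trial.** Let g = 14 or 11 days be the gap and L the number of days over which visits occur, spread evenly. The plan does not give L. The share of patients cut short is min(1, g/L). Mean days lost per enrolled patient is g²/(2L) when L ≥ g, and g − L/2 otherwise. Points missed = 5 × mean days lost / 42.

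| Enrolment length (assumed) | Share cut short | Mean days lost | Points missed |
|---|---|---|---|
| 7 days | 100% | 7.5 to 10.5 | 0.89 to 1.25 |
| 28 days | 39% to 50% | 2.2 to 3.5 | 0.26 to 0.42 |
| 84 days | 13% to 17% | 0.7 to 1.2 | 0.09 to 0.14 |

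The 7-day row applies only if the 1-week statement in Section 5.6 describes the whole enrolment period.

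**5. Effect on power.** At 1,100 per arm the detectable difference is 5.34 points from 25%, and 5.23 to 5.26 points from 23.3% to 23.7%. The change is negligible.

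**6. Extract date implied by the plan's own allowance.** One month of lag added after the endpoint window gives 42 + 28 = 70 to 42 + 31 = 73 days after the last target visit.

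**The case against.** The strongest reply is that this is a drafting slip with little practical risk. The sentence is broken, and the month may have been meant as the lag allowance for the visit-day primary outcome only, or as lag added after the 6 weeks. Outcomes come from standing records that hold vaccination dates, so no follow-up visit can be missed. An analyst building the 6-week variable that four sections call for would need data to day 42 and could still pull them while identifiers are held.

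Much of this stands as context. The harm arises only if Section 5.6 is followed, and it looks like an inconsistency more than a deliberate choice. But neither rescuing reading is in the text, which ends all collection of vaccination receipt and counts from the visit. The Study Schema (5.3) and the Aim 1 figure are not shown and might give a later extract; if they do, Section 5.6 would still contradict them.

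Two smaller objections also have force. The percentage-point losses rest on assumed accrual and enrolment patterns; only the 11 to 14 days come straight from the plan. The 7-day enrolment case is the least likely, because the 1-week statement can be read as the time from message to visit for one patient, and Section 4.3 describes rolling identification.

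Finally, because arms are assigned by visit day, the last-visit reading could leave somewhat different shares of truncated patients in the three arms. That would depend on how the days were drawn; the cut-off rule itself favours no arm.

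**Conclusion.** The concern holds. Section 5.6 conflicts with Sections 2, 5.2, 6.4 and 6.5.2, and neither way of counting its month guarantees every patient 42 days. The shortfall is 11 to 14 days for all patients if the month is per patient, and up to 11 to 14 days for those seen in about the last two weeks if it runs from the last visit and enrolment is longer than that.

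Under even accrual between the planning rates, the usual-care rate would be understated by 1.3 to 1.7 points in the first case. In the second it would be understated by roughly 0.1 to 0.4 points for enrolment of 12 down to 4 weeks, and by up to 1.25 points if enrolment lasted a single week. Refresh lag could widen the gap by an amount the plan does not fix.

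The primary endpoint is unaffected. This should be fixed before the extract is taken, but it does not threaten the trial's main result.

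**What to change.** Replace the collection sentence in Section 5.6 with wording such as: *Vaccination receipt will be ascertained through day 42 after each patient's target visit. The final extract will be taken after day 42 of the last patient plus a stated allowance for registry and EDW lag, and linkage identifiers will be kept until then.* If the existing month is kept as the allowance, the extract falls 70 to 73 days after the last target visit.

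The extract moves about 2 weeks later with no lag allowance, or 6 weeks later (42 days) with the 1-month allowance. Identifiers are held that much longer. Sections 5.7 and 9.5 already permit this, since they tie removal to milestones and not to dates. A change to the end-of-study definition may need IRB notification, as the study runs under a requested waiver. No patient contact, new data source or change in sample size is needed.

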5.7 Data sources

Sources of research material, data that will be recorded, when data will be collected

Data regarding patients' medical history, disease control, medication use and health care utilization will be obtained from The Mass General Brigham COVID-19 Vaccine Registry and EHR data from the Research Patient Data Registry (RPDR) and/or Enterprise Data Warehouse (EDW), supported by Epic Systems, Inc.

The Mass General Brigham COVID-19 Vaccine Registry is a secure repository of data containing COVID-19 vaccine administration, utilization and adverse event information for analysis by the research community. This registry contains identified patient vaccination data for patients with a record of any type or dose of the COVID-19 vaccine. The data lives on a secure server within the Mass General Brigham firewall. It is only accessible to IRB-approved researchers. The data in the registry is updated every week. Its usage is logged and audited.

The Enterprise Data Warehouse for Epic EHR data resides in an Oracle 9i environment and consists of the Clarity and Payer databases. The Clarity database is a relational database that contains clinical and financial information from the Epic Suite of products; including the electronic medical record system (EpicCare), the appointment scheduling system (Cadence), the patient accounting system (Resolute), the patient web portal and the master patient index (Identity). The various tables within the Clarity database are refreshed on a daily, weekly or monthly basis. The data extracts obtained from the RPDR/EDW are maintained on secure MGB servers housed at the Division of Pharmacoepidemiology in the Department of Medicine at BWH.

Linkages to subjects, access to subject identities

Individually identifiable data are required to link patients between the Mass General Brigham COVID-19 registry and the RPDR/EDW, and to send messages to patients as part of this trial. Without this linkage, we could not fulfill the study's objectives. To protect the confidentiality of these data, only the minimal necessary research staff will have access to personal identifiers. After the intervention is completed and study variables are created, all identifiable information will be deleted from the study database. All research staff are properly trained in research management and will be approved by the IRB. All personally identifiable health information will be kept under lock and key.

Schedule of activities

	Screening	Enrollment	Intervention	Analysis
Identification of eligible patients	X			
Randomization		X		
Control and experimental interventions			X	
Primary outcome analysis				X
Predictive modeling analysis				X

